## Overall Rationale and Organization

These clinical pharmacokinetic-pharmacodynamic experiments aim to establish  $\alpha 4\beta 2^*$  nAChRs as appropriate targets for treatment of levodopa resistant gait and balance deficits in hypocholinergic PD subjects. Subjects will be drawn from **Project II** and the **Clinical Resource Core**. In **SA1**, we will use  $[^{18}\text{F}]\text{flubatine}$  PET imaging to determine the lowest VCN dose producing high  $\alpha 4\beta 2^*$  nAChR occupancy. In **SA2**, we will use this dose to perform pharmacodynamic studies of VCN effects on laboratory measures of gait and postural control. These studies will determine if  $\alpha 4\beta 2^*$  nAChR stimulation produces the predicted effects on laboratory measures of balance and gait – directly addressing our central hypothesis. In **SA3**, we will study the effects of subacute VCN administration on a measure of attentional capacity sensitive to cholinergic deficits, testing our hypothesis that improvement in attention capacity will correlate with improvements in gait and postural control. These data will evaluate a likely physiological mechanism mediating the effects of stimulating  $\alpha 4\beta 2^*$  nAChRs in the context of the hypocholinergic PD brain, and provide important validation data for the rodent model used in **Project I**.

We propose subacute (days) VCN administration and focus on hypocholinergic PD subjects. Because repeated  $\alpha 4\beta 2^*$  nAChR stimulation, as would be experienced by chronically treated patients, induces functional receptor upregulation, assessing  $\alpha 4\beta 2^*$  nAChR occupancy with a single VCN dose in VCN naïve subjects will be misleading. Moreover, a VCN dose that produces high percent receptor occupancy in a VCN naïve subject may exhibit considerably less  $\alpha 4\beta 2^*$  nAChR occupancy in subjects exposed repeatedly to VCN and with  $\alpha 4\beta 2^*$  nAChR upregulation. It might be scientifically interesting to include normocholinergic PD subjects, but safety concerns hinder this approach. In our model (**Overview**; **Project I** data), dopaminergic striatal deficits result in compensatory “loading” of other brain systems. Normocholinergic PD subjects depend on increased cholinergic neurotransmission to compensate for striatal dysfunction, placing them at increased risk of adverse events resulting from reduced cholinergic signaling (32,46). VCN is a partial agonist with an efficacy of approximately 40% of ACh. In normal individuals, VCN produces measurable improvements on cognitive tests

(79,88), but in normocholinergic PD subjects, VCN may interfere sufficiently with  $\alpha 4\beta 2^*$  nAChR mediated compensation to produce functional impairments, including cognitive impairment and/or diminished balance, including damaging falls. It is not feasible to recruit sufficient subjects to do these experiments in an inpatient setting, which would be required to mitigate these potential side effects. For these reasons, we will not expose normocholinergic PD subjects to VCN. Beyond these important safety concerns, adding study groups to the proposed experiments would reduce statistical power for a fixed sample size, increasing the Ns required for a valid study beyond that which can be supported by funds available for Udall Center studies.

We will investigate the possibility that regulation of  $\alpha 4\beta 2^*$  nAChRs might be different in PD brain versus brains of normal individuals. We will investigate this possibility with a focused study of  $\alpha 4\beta 2^*$  nAChR receptor occupancy in a small group of normal subjects. Following the conclusion of receptor occupancy studies in hypocholinergic PD subjects, we will perform a more limited, parallel, dose-receptor occupancy study to determine if there are major differences in VCN receptor occupancy between PD and control subjects.

**Subject Selection:** PD subjects will be drawn from **Project II** subjects who have undergone  $[^{18}\text{F}]\text{FEOBV}$  imaging to identify cholinergic deficits.

We will study subjects with cortical innervation deficits below the 5th percentile cutoff of controls as defined previously (17). General inclusion and exclusion criteria are specified in the **Clinical Resource Core** and **Project II**. Current or previous (within last 6 months) use of any product or medication containing nicotinic agents, including use of tobacco products such as cigarettes, cigars, pipes, chewing tobacco, etc., e-cigarettes, OTC nicotine patches, chewing gum containing nicotine, or varenicline is an exclusion. While most data does not indicate that VCN causes suicidality or cardiovascular problems (73 - 81), we will exclude subjects with depression, active cardiovascular disease, history of seizures, or alcohol use disorders. (see **Human Subject Protection**).

[figure not shown]
The **Clinical Resource Core** and **Project II** project initial enrollment of 95 PD subjects with longitudinal follow-up of 75 PD subjects. Based on prior results, we project that 30% (32) of the initially enrolled subjects will be hypocholinergic. Based on preliminary data (**Project II**), 25% (20) of the longitudinally followed PD subjects will convert from normo- to hypocholinergic during the project period. This gives a total of 52 eligible subjects (Table 1). Our long-standing experience is that a significant fraction of subjects participate in multiple experiments, so we anticipate little difficulty in recruiting the projected 55 PD subject-equivalents required. In our recently concluded Program Project Grant (NS15655), we studied 151 PD subjects. All underwent at least 2 PET studies with 112

undergoing 3 or more scans (69 - 3 studies; 43 - 4 studies). We are basing our estimates on a stringent 5th percentile cut-off relative to our normal control database. We will carefully monitor subject recruitment to enroll the target number of hypocholinergic PD subjects. If needed, **Core B** will preferentially recruit an enriched sample of PD subjects with longer duration disease and/or mild cognitive changes, subjects more likely to exhibit cholinergic deficits. **Core B** will be aided in recruitment by the **Core D** (Education and Outreach Core). **Appendix 1** contains a detailed schedule of study activities.

**IND Exemption:** We obtained an IND exemption from the FDA.

**Specific Aim 1:** To use [F]flubatine PET to assess VCN occupancy of brain  $\alpha 4\beta 2^*$  nAChRs after subacute VCN administration to the subgroup of PD subjects with cholinergic deficits.

**Rationale and Predictions:** We will use [F]flubatine PET to select an appropriate VCN dose for **SA2** and **SA3** studies. Application of [F]flubatine PET will allow selection of the lowest dose producing high (>90%) receptor occupancy. Measuring VCN displacement of [F]flubatine obviates the need for clinical dose escalation studies in hypocholinergic PD subjects.  $\alpha 4\beta 2^*$  nAChRs are complex heteromeric proteins with highly regulated expression and function. These studies are essential, as the PD brain is a very different environment from a normal brain. We predict that these studies will identify a VCN dose at the lower end of the clinically used range producing high (>90%)  $\alpha 4\beta 2^*$  nAChR occupancy. A recent acute VCN dose study in acutely abstinent smokers (upregulated  $\alpha 4\beta 2^*$  nAChRs) with [F]FA-85380 reported that a single 0.5 mg

**Figure 3:** [F]flubatine PET. Left Panel: averaged late frame images of a control subject. High binding in thalamus, striatum, cerebellum, and frontal cortex. Right Panel: Typical time-activity curve for a control oral VCN dose (typical treatment dose = 1 mg bid) produced ~95% receptor occupancy with imaging several hours after ingestion (70). This result suggests strongly that lower clinical VCN doses will produce high (>90%) receptor occupancy. All subjects will undergo baseline [F]flubatine scanning after subacute VCN treatment to induce upregulation and following VCN washout to allow measurement of per cent VCN occupancy of upregulated  $\alpha 4\beta 2^*$  nAChRs.

**Preliminary Data:** Our PET Center is performing [F]flubatine imaging on a routine basis (**Figure 3, Table 2**). [F]Flubatine PET has regional distribution expected for  $\alpha 4\beta 2^*$  nAChRs, excellent signal to noise properties, and imaging can be completed in 90 minutes. Notably, regional binding values are highly reproducible across subjects with low coefficients of variation (**Table 2**). **Procedures:**  $\alpha 4\beta 2^*$

nAChR expression will be measured *in vivo* with [F]flubatine. Subjects will receive varying VCN doses. [F]Flubatine imaging will be done 10 days after initiation of VCN administration and 5 days after VCN discontinuation (**Figure 4**). The difference between [F]flubatine binding before and after VCN discontinuation will be measured to assess  $\alpha 4\beta 2^*$  nAChR occupancy. Receptor occupancy will be assessed in regions exhibiting high  $\alpha 4\beta 2^*$  nAChR expression; thalamus, striatum, and cerebellum, as results are likely to be more variable in regions with lower  $\alpha 4\beta 2^*$  nAChR expression. Based on prior animal and human studies, 7-10 days is adequate to induce receptor upregulation (91-95). VCN has a  $t_{1/2}$  of ~24 hours and 10 days will be adequate to attain equilibrium and induce upregulation. VCN pharmacokinetics (PK) do not change with age and absorption is unaffected by food (96). Five days is adequate to clear VCN.  $T_{\text{max}}$  is 2-4 hours post oral administration. The first scan will occur in the afternoon of day 10 after the morning VCN dose to avoid peak dose effects which could increase variance.

The recommended clinical VCN dose schedule is 0.5 mg per day for 3 days, followed by 0.5 mg bid for 4 days, followed by 1 mg bid. Mocking et al. recently reported positive neuropsychological results of subacute VCN

**Table 2:** [F]Flubatine binding values for regions expressing high levels of  $\alpha 4\beta 2^*$  nAChRs. N = 3 controls. DVR = Distribution Volume Ratio; SD = Standard Deviation; COV = Coefficient of Variation.

Region	Mean DVR	SD	COV
Thalamus	1.57	0.11	6.9%
Striatum	0.90	0.02	2.1%

treatment (0.5 mg/day for 3 days, then 1 mg/day for 4 days) in normal controls (79). Because we are administering VCN to a clinical population and not young, healthy controls, we propose lower initial doses than Mocking et al. We will start with 0.25 mg/day on a subacute treatment schedule of 10 treatment days. A potential acute side effect of VCN is nausea, though this is unusual in non-smokers with doses below 1 mg per day. To reduce the chance of nausea or other side-effects, we will use a series of escalating dose schedules (**Appendix 2**). VCN will be prepared by the U-M Health System Research Pharmacy. VCN pills are small, easily encapsulated in gelatin capsules, and will be dispensed in blister packs to facilitate administration and compliance monitoring. The initial maximum dose studied will be 0.25 mg/day. Subsequent, projected maximum doses are 0.25 po bid, 0.5 mg po bid, and 1 mg po bid (if needed). Twice daily dosing is used to minimize peak dose effects. We anticipate 3 dose points, each consisting of 3 participants (total of 9

[figure not shown]

Figure 4: Timeline of SA1 Experiment

participants), to establish the required oral dose for **SA2** and **SA3** experiments. The results of the initial (0.25 mg/day maximum dose) study will be used to select the next dose point. If there is a substantial effect on [F]flubatine binding (>50% reduction), we will use the 0.25 mg bid maximum dose schedule for the next experiment. If the effect on [F]flubatine binding is <50% reduction, we will use 0.5 mg bid maximum dose schedule for the next experiment. Selection of the subsequent dose schedule will be based on the results of the 0.5 mg bid maximum dose experiment. We will increment dose schedules until there is no additional reduction in [F]flubatine binding, i.e., remaining binding is non-specific binding, and the penultimate maximum dose defines our **SA2-SA3** study dose. Based on the work of Lotfipour et al., who found that a single oral 0.5 mg VCN dose produced ~100% receptor occupancy (70), we don't anticipate using the highest (1 mg po bid) dose schedule). We will measure plasma VCN levels at the time of the initial scan (Pharmacokinetics Core, U- M College of Pharmacy; see attached letter from [name], Core Director). These measurements are not for formal PK studies as VCN PK is well established, but rather to confirm study drug compliance. We aim to establish the lowest dose producing high (~100%) receptor occupancy and if we achieve this goal after studying 2 dose schedules (6 participants total), we will stop and proceed to **SA2** experiments.

PD Subjects will continue their customary PD treatments. Subjects will be evaluated in the University of Michigan Functional Neuroimaging, Cognitive and Mobility Laboratory (see **Facilities & Resources**). All subjects will undergo a standard clinical and brief psychometric evaluation immediately prior to VCN treatment initiation, at the time of initial scan and at the time of the second scan. Subjects will undergo a MDS-UPDRS, Geriatric Depression Scale, Montreal Cognitive Assessment, WAIS Digit Span and Digit Symbol coding tests, and D-KEFS executive function/working memory tests. Subjects will be screened for suicidality with the Columbia Suicide Severity Rating Scale (C-SSRS; <http://www.cssrs.columbia.edu/>) before VCN treatment and at the time of each PET study. [name] is certified in use of the C-SSRS (**Appendix 3**) and [name] and other relevant members of the Clinical Resource Core will also become certified. Subjects will be directly observed for 3 hours after their initial VCN dose, with phone follow-up the next day and weekly thereafter. Subjects will be screened for history of seizures and alcohol abuse. The latter will be assessed with the WHO Alcohol Use Disorder Identification Test (AUDIT). Per the WHO guidelines, individuals with scores >8 (ages 18-65) or >7 (ages >65) will be excluded. Individuals with a history of seizures will be excluded. Participants will be advised to refrain from alcohol use during study participation. An investigator ([name] or [name]) will be on-call for subject concerns at all times. Data will be recorded on standard CRFs and entered into the database for management and analysis by the **Biostatistics and Data Management Core**. Adverse events will be classified by organ system and assessed for causality. All potential possible adverse events will be discussed by the Udall Center Executive Committee acting as DSMB, and reported promptly to the IRB and NINDS.

Following completion of the PD subject study experiment 1, we will perform a limited experiment to assess  $\alpha 4\beta 2^*$  nAChR occupancy in age-matched controls. Controls will receive VCN (no placebo) for 10 days. We will select a subset of the doses used for the PD subjects in experiment 1 to assess receptor occupancy in normal controls. Assuming we don't detect very high (>90%) occupancy with our initial dose (0.25 mg/day), we will expose controls to one of three different dosages of varenicline to construct a dose-occupancy relationship for comparison with the results in PD subjects. Based on the results of experiment 1, experiment 2 will include the following dosages

with a goal of 3 patients per cohort: .25mg QD, .25mg BID and .5mg BID. All procedures will be identical to experiment 1. Control subjects will be drawn from the normal control pool characterized concurrently in the Clinical Core of the Udall project, much as the PD subjects are drawn from the pool of PD subjects. Control subjects will also be recruited from the UM Health Research website if needed. We anticipate studying 9 subjects, 3 at each dosage point. To adjust for potential dropouts, we will budget 12 control subjects.

**Potential Problems and Alternatives:** The results of Loftipour et al. suggest that low doses will produce high  $\alpha 4\beta 2^*$  nAChR occupancy (70). Commercially available VCN pills are small and division beyond bisection is likely to be inaccurate. 0.25 mg/day is the lowest feasible dose and if we find this dose produces high per cent receptor occupancy, no further testing will be necessary. VCN tolerability may be a problem as this agent has not been tried specifically in PD subjects previously. To avoid any problems, we are starting with low doses and using an incrementing schedule. Nausea was infrequent in a recent trial in AD which used significantly higher doses (89). If tolerability is an issue, then we will alter the incrementing schedule to more gradually “ramp” up to the desired dose.

**Specific Aim 2: To assess the effects of pharmacologic  $\alpha 4\beta 2^*$  nAChR activation on laboratory measures of gait function and postural control in PD subjects with cholinergic deficits.**

**Rationale and Predictions:** The central hypothesis of this project is that deficient activation of  $\alpha 4\beta 2^*$  nAChRs consequent to the degeneration of cholinergic projections causes balance and gait abnormalities in PD. Consequently, restoration of  $\alpha 4\beta 2^*$  nAChR stimulation should improve these deficits. In this target engagement pharmacodynamic experiment, we will evaluate the effects of the  $\alpha 4\beta 2^*$  nAChR partial agonist VCN on laboratory measures of gait function and postural control in hypocholinergic PD subjects. We predict that subacute VCN administration will improve gait function and postural control in hypocholinergic PD subjects. We chose a pair of relevant physiologic endpoints; gait speed and Horak's JERK (97,98,99). Slow gait is a cardinal sign of PD and we demonstrated recently that slowed gait is strongly associated with neocortical cholinergic denervation (56). Similarly, Rochester et al. found that gait speed in PD correlated with an indirect clinical electrophysiologic measure of cortical cholinergic function (100). Slowed gait is also a feature of our combined dopaminergic-cholinergic rat model (32). We will apply the Instrumented test of postural Sway (ISway; APDM Mobility Lab; <http://apdm.com/gait-and-posture/Mobility-Lab/index.html>), a relatively simple and robust method for evaluating postural control with a belt-worn inertial sensor (97,98,99). ISway was developed specifically to assess postural control in PD subjects and is validated against more complex methods. Abnormalities of these types of measures are associated in both cross-sectional and prospective studies with increased fall risk in the elderly, and measure relevant postural control phenomena in

PD (101-104). JERK is one of several parameters measured by ISway, captures postural sway irregularity, and possesses strong validity, good test-retest behavior, and good correlation with UPDRS III PIGD scores (97).

**Preliminary Data:** Our group implemented the ISway system in the Functional Neuroimaging, Cognitive and Mobility Laboratory (**Table 2**). We studied 11 similar PD subjects, 6 with a history of falls and 5 without any fall history. ISway measures of postural control differentiated fallers and non-fallers (**Table 2**).

**Procedures:** The **SA1** experiment will select the VCN dose. Based on discussions with the proposed **Biostatistical and Data Management** co-Core leaders, we will employ a randomized double-blind, placebo-controlled, 2-period, 2-sequence crossover design to assess the effects of subacute VCN administration on gait function, postural control, and attention in PD subjects with cholinergic deficits (**Figure 5**). PD participants will be on stable doses of dopaminergic therapy for 3 months prior to enrollment and continue on their usual

schedule of dopaminergic medications for the duration of this study. Individuals with depression and unstable cardiac disease will be excluded. Within-subjects crossover designs were employed successfully in recent VCN trials for AD and mood disorders during smoking cessation (89,90).

[figure not shown]
We will administer VCN or placebo for 3 weeks, followed by a 3 week washout period, and crossover to placebo or VCN for the 3 week second treatment period. Study visits will be completed within a five business day window before or after the target date. The duration of the treatment and washout periods is based partly on prior human experimental and trial experience (89-95). Mocking et al. detected improved cognitive effects of VCN with a week of treatment (79). We chose a longer period to ensure stable receptor upregulation and because initiation of treatment may require gradual dose incrementing. The washout period is based partly on work by Zhang et al. with another  $\alpha 4\beta 2^*$  nAChR partial agonist in MPTP lesioned non-human primates (71). This group reported an effect of

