Gait speed and postural control will be assessed at baseline, at the end of the first VCN/placebo administration period, at the end of the washout period, and at the end of the second VCN/placebo administration period. Gait and postural control will be assessed by the **Clinical Resource Core (Core B)** using the Mobility Lab system that is already established (see Table 3; methodology for Mobility Lab will be as described in detail in Project II). MDS-UPDRS, Geriatric Depression Scale, Montreal Cognitive Assessment, WAIS Digit Span and Digit Symbol coding tests, and D-KEFS executive function/working memory tests will be administered as part of the evaluations. Subjects will be screened for suicidality with the C-SSRS before VCN treatment, weekly during phone follow-up, and at the end of treatment-washout periods.

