4.1 General Study Design and Plan

The goal of the first experiment was to select the lowest dose of VCN to produce high (90%) receptor occupancy. $\alpha 4\beta 2^*$ nAChR receptor occupancy is defined as the difference between [¹⁸F]Flubatine binding before and VCN discontinuation, i.e., 10 days after initiation of VCN administration (Day 10) and 5 days after VCN discontinuation (Day 15).

The goal is to have 3/3 subjects achieve >90% receptor occupancy. The dose schedule will be increment, as shown in the figure above, until there is no additional reduction in [18F]Flubatine binding, i.e., remaining binding is non-specific binding, and the penultimate maximum dose will define the dose to be used in the future crossover study.

The second experiment replicates the first experiment in a healthy volunteer population, matched for age. This experiment occurred after the results of the first experiment were known. Thus, only 3 dose groups were assess: 0.25 mg QD, 0.25 mg BID and 0.5 mg BID.

Participants received their first dose of varenicline on Day 1, followed by dose escalations on days 2 and 3 (as needed). On Day 10, they discontinued varenicline and received their first flubatine PET scan. Five days after discontinuation of varenicline (Day 15), they received their second flubatine PET scan.

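### In SA1 the stated C-SSRS and GDS schedule has no screen between the first varenicline dose and the last dosing day; giving the C-SSRS at the weekly call already planned would add one at little cost (minor)

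*Protocol*

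**What the plan says.** The Protocol, Specific Aim 1, Procedures, schedules the C-SSRS "before VCN treatment and at the time of each PET study". The GDS belongs to the clinical and psychometric evaluation, which takes place "immediately prior to VCN treatment initiation, at the time of initial scan and at the time of the second scan". After three hours of observation following the first dose, subjects are contacted "with phone follow-up the next day and weekly thereafter". No instrument is named for those calls.

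Varenicline (VCN) is given on "a subacute treatment schedule of 10 treatment days". On timing, the same section states: "The first scan will occur in the afternoon of day 10 after the morning VCN dose". SAP 4.1 agrees: "On Day 10, they discontinued varenicline and received their first flubatine PET scan". The second scan is on Day 15. For the control experiment the Protocol states: "All procedures will be identical to experiment 1".

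In the crossover (Specific Aim 2, Procedures) the C-SSRS is given "before VCN treatment, weekly during phone follow-up, and at the end of treatment-washout periods".

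The Mood Disorders paragraph of the Protocol's Protection Against Risk section contains the safety action. VCN is stopped at once if mood worsens or suicidal ideation appears, and the investigators promptly assess anyone whose GDS score worsens. The paragraph promises regular assessment with both scales and refers the reader to the Approach section and to a Schedule of Activities in the Appendix.

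**The concern.** The stopping rule is the plan's stated protection against a risk that carries a boxed warning. A scheduled screen serves that rule best while dosing can still be shortened. In SA1 the first screen on drug coincides with the day dosing ends, so a worsening GDS score or a positive C-SSRS item can first be recorded when there is almost nothing left to stop. Before then, detection rests on calls of unspecified content and on what the participant volunteers.

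The crossover text shows that the sponsor accepts C-SSRS administration by phone and considers weekly screening on drug appropriate. SA1 already has the calls, and the Protocol gives no reason for leaving the instrument out of them.

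There is a smaller reporting consequence. SAP 9 plans a descriptive C-SSRS summary by cohort and dose group. On the stated schedule it would hold one on-drug value per participant, taken on the last dosing day.

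**Working it through.** This is a day count; no power or error-rate calculation is involved, and the plan gives no figure of its own to reproduce.

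**Inputs.** First dose on Day 1 (SAP 4.1). Ten treatment days, and scans on Days 10 and 15 (Protocol, SA1 Procedures; SAP 4.1). C-SSRS and GDS before VCN and at each scan; calls the next day and then weekly (SA1 Procedures). Crossover periods of three weeks, with a first call 1 to 2 business days after the start, weekly calls after that, and an end-of-period blood draw on Day 22 (Specific Aim 2, Procedures).

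**Step 1, stated SA1 screens.** They fall before the first dose, on Day 10 and on Day 15. Screens after the first dose and before Day 10: 0. Interval from first dose to first on-drug screen: 10 − 1 = 9 days.

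**Step 2, what Day 10 can still do.** The scan follows the morning dose. On a twice-daily schedule a Day 10 screen could prevent one evening dose, if one were due. SAP 4.1 has VCN discontinued that day, so the remaining scope is one dose at most.

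**Step 3, SA1 calls already planned.** The next-day call is Day 2. The weekly call is Day 1 + 7 = Day 8 or Day 2 + 7 = Day 9, depending on where counting starts. Either way, two calls fall before Day 10.

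**Step 4, crossover comparison.** Weekly calls fall on about Days 8 to 10 and 15 to 17, so there are about 2 weekly C-SSRS screens before Day 22. The first comes 7 to 9 days after the start. The interval to the first on-drug screen is therefore much the same in both parts; the difference is that SA1 dosing ends at that point.

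**Step 5, effect of adding the C-SSRS to SA1 calls.**

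| SA1 schedule | Screens before Day 10 | On-drug C-SSRS values (including Day 10) | Intervals from Day 1 to Day 10 (days) |
|---|---|---|---|
| As stated | 0 | 1 | 9 |
| Weekly call added | 1 | 2 | 7, 2 or 8, 1 |
| Next-day and weekly calls added | 2 | 3 | 1, 6, 2 or 1, 7, 1 |

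A Day 8 screen leaves 2 days before Day 10, and a Day 9 screen leaves 1. A Day 2 screen leaves 8.

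**Step 6, drift.** The crossover allows its calls a window of two business days either side. If SA1 used the same window, a Day 8 or 9 call could move to Day 10 or later and the gain would be lost.

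**The case against.** The strongest objection is that the full schedule is not in view. The Mood Disorders paragraph points to an Appendix schedule for exactly these two scales. Appendix 1 is described as the detailed schedule, and the SA1 timeline figure is not shown. The Appendix may already contain what is proposed here. That stands, and it limits the point to the SA1 text. It does not remove it, because that text sets explicit C-SSRS times rather than leaving them open, and those times differ from the crossover's.

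Second, a reader might infer that participants go unmonitored for nine days, or that the stopping rule cannot operate before Day 10. The documents do not support either reading. The rule needs no scale score. SA1 has three hours of observation, two staff-initiated calls and an investigator always on call. Participants are told of the boxed warning and asked to page with concerns, and SAP 4.5 collects adverse events over all 15 days. Entry screening removes active, significant mood disorder. What is missing is a named instrument, not contact.

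Third, a reader might infer that the plan's own practice calls for two extra screens. It does not. The crossover text specifies the C-SSRS at weekly calls and does not name it for the first call. The precedent supports one added screen; a Day 2 screen would be an extension.

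Fourth, the gain is small: a Day 8 or 9 screen can spare only the last day or two of dosing. That also stands, and it is why the point is minor.

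Finally, control doses were set from the PD results, and SAP 4.1 says the control experiment followed once those results were known. The PD part may therefore already be finished, and new wording may reach only controls.

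**Conclusion.** The point holds as a minor, inexpensive improvement to safety monitoring. On the SA1 text, no named mood or suicidality screen falls between the first dose and the last dosing day, and a Day 10 screen could at most prevent one evening dose. Using the weekly call as the crossover does changes the count from 0 to 1; using the next-day call as well changes it to 2.

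It would be wrong to call this a serious safety defect. Doses are low, exposure is 10 days, unstructured cover is in place and absolute risk is probably low. No endpoint, dose decision or inference depends on it.

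The conclusion assumes that Appendix 1 adds no SA1 screen, that Day 1 is the first dose, and that some participants remain to be dosed.

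**What to change.** Add to the Protocol, Specific Aim 1, Procedures: *C-SSRS-certified staff will also administer the C-SSRS at the weekly phone call, made no later than Day 9, to all participants still to be dosed, including controls.* The fixed latest day keeps the call within dosing. The change is confined to the C-SSRS because the documents describe no phone use of the GDS.

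Optionally, give it at the next-day call too. That leaves more dosing time in which stopping would matter, but it goes beyond the crossover precedent.

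If Appendix 1 already schedules such a screen, align the SA1 text with it. If SA1 dosing is complete, as the SAP's past tense suggests it may be, report whether the calls included the C-SSRS.

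**Cost.** One sentence, with no new visit or call. At an assumed 5 to 10 minutes per administration:

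- Controls only, 9 to 12 as the Protocol plans (the SAP gives 10), one call each: 9 × 5 = 45 minutes to 12 × 10 = 120 minutes in total.
- All of SA1, 9 to 12 PD (3 dose points × 3 in the Protocol or × 4 in the SAP) plus 9 to 12 controls = 18 to 24 participants, one call each: 18 × 5 = 90 minutes to 24 × 10 = 240 minutes, or 1.5 to 4 hours.
- All of SA1 with both calls: 36 × 5 = 180 minutes to 48 × 10 = 480 minutes, or 3 to 8 hours.

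The calls would need C-SSRS-certified staff; the Protocol already plans to certify more.
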